5.4. Statistical Section

The primary objective of the trial is to determine if there is a difference in overall survival among patients with limited gastric cancer metastases who are randomized to receive either systemic therapy alone or gastrectomy, metastasectomy and systemic therapy.

Based upon results in the literature, patients who would be eligible for this trial and who receive systemic therapy alone would be expected to have an estimated 12-month median overall survival from the date of randomization. The goal of this study will be to determine if the use of gastrectomy, metastasectomy and systemic therapy will result in an 8-month increase in overall survival, to a median of 20 months. Patients will be randomized between systemic therapy alone or gastrectomy, metastasectomy and systemic therapy and followed for overall survival. Kaplan-Meier curves and a two-tailed log-rank test will be the primary analysis methods. Assuming exponential overall survival curves, the hazard rate for the systemic therapy is 0.0578, or approximately a 5.8% probability of death each month when the median survival is 12 months. If we assume that the surgery plus systemic therapy arm has a median overall survival of 20 months, this corresponds to a hazard rate of 0.0347, and the resulting hazard ratio for the comparison of the two overall survival curves would be 1.67. To compare these curves and detect a difference with a 0.05 two-tailed log-rank test, a total of 68 evaluable subjects per arm (136 total) will need to be enrolled over a 6-year period and followed for an additional 2 years from the date of entry of the last patient, with 121 total deaths, in order to have 80% power to compare the curves.

Patients will be stratified for site of metastases (liver, peritoneal, or lung), disease-free survival and prior systemic therapy for gastric metastases.

Progression-free survival will also be evaluated using Kaplan-Meier curves, and a two-tailed log rank test, as a secondary endpoint. In addition, a prognostic factor evaluation using Cox proportional hazards modeling will take place after the study has concluded in order to identify if there are factors which can be identified that are associated with survival or progression free survival in patients randomized to treatments on this trial; this will also be interpreted as a secondary endpoint.

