The study will be monitored by the NCI/CCR Data Safety and Monitoring Board on an annual basis to evaluate the safety of the two arms. The SAEs (typically grade 3 toxicities, or greater) will be reported according to type of toxicity, and maximal grade noted per patient, for toxicities with at least a possible attribution to the therapy provided on that arm. Comparisons will be made between the two arms using Cochran-Armitage tests for trend, or other appropriate methods, to determine if there is increased toxicity associated with either arm.

In addition, at the first Data Safety and Monitoring Board (DSMB) meeting held following the point at which half of the required total subjects have been enrolled (68 total), a single evaluation for futility will be undertaken. Evaluations for better than expected efficacy will also be made annually, beginning after half the subjects have been enrolled.

The futility evaluation will be performed as follows: based on the full data available at the time, a conditional power analysis will be performed to determine if the trial is unlikely to find an effect at the 0.05 two-tailed significance level with continued accrual based on an overall survival endpoint. Median survivals of 12 and 20 months correspond to 12-month survivals of 50% and 66% respectively. Using these as the values under the alternative, and using the actual proportions alive at 12 months, based on the observed fractions and the expected sample sizes at 12 months, the conditional power of the trial will be determined assuming accrual of the remaining patients to achieve a total of 136 patients. If the conditional probability of finding a difference at the two-sided 0.05 level at the conclusion of the trial is less than 20%, then it will be reasonable to recommend that no further patients will be enrolled.

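### The futility calculation is written in 12-month survival proportions and names no final test, although the trial's primary test is a log-rank test on 121 deaths

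*Combined protocol and SAP*

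**What the plan says.** Section 5.4 makes the log-rank test primary: "Kaplan-Meier curves and a two-tailed log-rank test will be the primary analysis methods". The sample size is set "with 121 total deaths, in order to have 80% power to compare the curves". For the annual efficacy looks, the same section measures information as deaths divided by 121 and expects monitoring to start at roughly 40–45 deaths.

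The futility paragraph asks whether the trial is "unlikely to find an effect at the 0.05 two-tailed significance level with continued accrual based on an overall survival endpoint". It then lists its inputs. The alternative is given as "Median survivals of 12 and 20 months correspond to 12-month survivals of 50% and 66% respectively". The calculation then runs: "Using these as the values under the alternative, and using the actual proportions alive at 12 months, based on the observed fractions". The sample sizes are also those at 12 months ("based on the observed fractions and the expected sample sizes at 12 months"), and the trial is projected to 136 patients. The decision rule reads: "If the conditional probability of finding a difference at the two-sided 0.05 level at the conclusion of the trial is less than 20" per cent, "then it will be reasonable to recommend that no further patients will be enrolled".

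The paragraph mentions no interim log-rank statistic, death count or information fraction. Section 5.5 confirms that futility is evaluated once, at the first review of outcomes.

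**The concern.** Conditional power is the chance that a specified final test will reject, given the data so far. The paragraph does not specify that test, and its numerical inputs belong to a comparison of 12-month proportions, which the trial does not plan to make. A statistician who works from the listed inputs would naturally project a two-proportion test at 68 per arm. One who works from the stated endpoint would project the log-rank test on 121 deaths, and would find no instruction on how 12-month proportions enter it.

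The two calculations start from very different power, so they can give opposite advice on the same data. There is only one futility look, with about a third of the deaths observed. If the method is left open, the choice falls to whoever prepares the DSMB report, possibly after the data have been seen.

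**Working it through.** **Inputs.** From Section 5.4: medians 12 and 20 months, two-sided 0.05, 80% power, 121 deaths, 68 per arm, 24 patients a year. From Sections 5.4 and 5.5: DSMB reviews at least annually, so the look falls 0–12 months after patient 68. Assumptions: exponential survival (as in the plan), uniform accrual, no loss to follow-up, future patients following the 12 and 20 month medians, and a final critical value of 1.96 (efficacy looks ignored).

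**1. The plan's own figures.** Hazard ratio = 20/12 = 1.667. Deaths = 4(1.96 + 0.8416)²/(ln 1.667)² = 31.40/0.2609 = 120.3, so 121. Drift θ = √(121/4) × 0.5108 = 2.81, and power = Φ(2.81 − 1.96) = 80.2%. Twelve-month survivals are 50% and 0.5^(12/20) = 66.0%. With 72 months of accrual and 24 of follow-up, 121.1 deaths are expected. The stated figures reproduce.

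**2. State of the trial at the look.** Patient 68 enters at 68/24 × 12 = 34 months. Patients per arm with 12 months of follow-up at month T number 24(T − 12)/12/2. That gives 22, 28 and 34 per arm at 0, 6 and 12 months after patient 68, with about 33, 43 and 53 deaths expected. The plan's 40–45 deaths fall about 4.5–7.5 months after patient 68.

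**3. Inputs read as a two-proportion projection.** At 68 per arm, the pooled z test of 0.50 against 0.66 has power Φ[(0.16 − 1.96√(2×0.58×0.42/68))/√((0.25+0.2244)/68)] = Φ[(0.160 − 0.166)/0.0835] = 47% (46.6% by exact enumeration). For 80% power it needs 149 per arm. Exact enumeration, with remaining patients at 0.50 and 0.66, gives conditional power below 20% under the design alternative in 16.4%, 20.1% and 23.1% of trials with 22, 28 and 34 per arm.

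**4. Conditional power of the planned log-rank test.** With t = deaths/121 and interim statistic Z,

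CP = 1 − Φ[(1.96 − Z√t − 2.81(1 − t))/√(1 − t)].

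At 42 deaths, t = 0.347. CP is below 0.20 when Z√t < 1.96 − 2.81 × 0.653 − 0.8416 × 0.808 = −0.554, so Z < −0.94. The observed hazard ratio must then be at or below exp(−0.94 × 2/√42) = 0.75 on the plan's 1.67 scale, which favours SA. Under the alternative Z√t has mean 2.81 × 0.347 = 0.975 and SD √0.347 = 0.589, so the chance is Φ(−2.60) = 0.5%. It is 0.4% at 40 deaths and 0.6% at 45.

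**5. Simulation, 20,000 trials under each hypothesis.** Share of trials meeting the 20% criterion:

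| Look after patient 68 | 12-month, GYMS works | Log-rank, GYMS works | 12-month, null | Log-rank, null |
|---|---|---|---|---|
| 0 months | 16.4% | 0.2% | 55% | 12% |
| 6 months | 20.2% | 0.65% | 65% | 27% |
| 12 months | 23.0% | 1.4% | 72% | 46% |

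The formula in step 4 gives 0.1% at 33 deaths, hence the overall log-rank range of 0.1–1.4%.

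**6. One data set, two answers.** Suppose 27 per arm have 12-month status, with 14 alive on SA and 15 on GYMS. The two-proportion projection gives conditional power 18.7%, so the criterion is met. The implied hazard ratio is ln(14/27)/ln(15/27) = 1.12. At 42 deaths that gives Z = ln(1.12) × √42/2 = 0.36 and log-rank conditional power of about 54% (52–56% over 40–45 deaths).

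**7. Effect on power.** Full power in the simulation is 79.7%. If the 12-month projection is always followed, and enrolled patients are still followed and tested by log-rank at 0.05, power is 71.9–72.7% with 24 more months of follow-up. It is 73.1–74.2% with follow-up to the planned end.

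**The case against.** The log-rank reading is well supported. The paragraph speaks of the full data available, an overall survival endpoint and the conclusion of the trial, and no two-proportion test is planned anywhere. The two-proportion projection also ignores patients without 12-month status (about 12 of 40 per arm at six months), which sits badly with using all the data. This stands. A reader might infer that the plan has adopted a two-proportion futility test; the documents do not say so. The defect is that the listed inputs do not lead to the test the wording suggests.

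The rule is advisory, applies once, closes enrolment only and does not inflate type I error. The DSMB will also have deaths/121 at the same review. This stands too, and makes the harm conditional.

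A reader might also count every stopped trial as negative, which would put power at about 66–70%. The documents do not support that. Section 3.10 commits to lifelong follow-up and does not list accrual closure as a reason to leave the study, and the Precis specifies intention-to-treat survival analysis. What stays unstated is when the final log-rank test would be run after early closure.

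The example in step 6 lies near the boundary: 16 survivors on GYMS instead of 15 gives 25.5%. It shows that the calculations can disagree, not how often. On frequency, at the six-month look 97% of the effective trials flagged by the 12-month projection had log-rank conditional power of 20% or more (median 61%).

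**Conclusion.** The point holds and should be fixed. As written, the futility paragraph does not determine its own calculation. With GYMS working as designed, the criterion is met in about 16–23% of trials on the 12-month projection (pooled z test, look 0–12 months after patient 68). On the planned log-rank test it is met in about 0.1–1.4%, or 0.4–0.6% at 40–45 deaths. The loss of power from 80% to about 72–74% requires that the 12-month reading is used, that the DSMB follows it, and that GYMS has exactly the design effect.

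The figures move with further choices the text leaves open. A Fisher or continuity-corrected final test raises the 12-month range to about 23–32%. Converting 12-month rates to a hazard ratio and projecting a log-rank test gives about 0–7%, depending on the information fraction. Projecting the observed trend instead of the design effect raises the log-rank figure to about 16–21%, but the paragraph's reference to values under the alternative points to the design effect. A final critical value above 1.96, as the O'Brien-Fleming looks imply, raises the log-rank figures slightly. With an assumed 2.00, the 42-death threshold becomes −0.514 and the chance Φ((−0.514 − 0.975)/0.589) = 0.6%.

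**What to change.** Replace the 12-month calculation in Section 5.4 with wording such as: *Conditional power is computed for the final two-sided log-rank test at 121 deaths, at the final critical value left by the O'Brien-Fleming spending function, from the interim log-rank Z, t = deaths/121, and hazard ratio 1.67 for the remaining deaths.* In the formula of step 4, that critical value takes the place of 1.96. Report the stopping probabilities under the null and the alternative, and say when the final log-rank test is run if accrual closes early. If a 12-month rule is truly intended, name its final test, say how 12-month survival and information are computed, and report its stopping probabilities and the reduced power.

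The cost is one paragraph and no new data, since deaths/121 is already needed at the same review. The downside is less stopping of null trials at an unchanged 20% cut-off: about 27% against 65% at six months after patient 68. A higher log-rank cut-off can recover this. A cut-off of 0.50, used here only to match null stopping (66%), flags 8.1% of effective trials, against 20.2% for the 12-month projection. Which cut-off to use is for the sponsor and DSMB to decide.

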1.1. Study Objectives

1.1.1. Primary Objective:

- To determine whether a therapeutic approach that includes gastrectomy and/or metastasectomy plus systemic therapy is superior to the standard of care approach that includes systemic therapy alone in terms of overall survival for patients who present with limited metastatic gastric cancer (MGC).

1.1.2. Secondary Objectives:

- To compare progression-free survival (PFS) between the two study arms
- To analyze prognostic factors and generate potential selection criteria for patients who present with limited gastric cancer metastases that might benefit from gastrectomy and/or metastasectomy plus systemic therapy.
- To analyze prognostic factors and generate potential selection criteria for patients who present with limited gastric cancer metastases that will not benefit from gastrectomy and/or metastasectomy.
- To determine if surgical resection impacts the dosing and duration of subsequent chemotherapy administration
- To compare quality of life (QOL) parameters between the two study groups. We will use tools specifically developed for assessment of QOL in gastric cancer patients: FACT-Ga, EORTC QLQ-STO22 and the SROTC QLQ-C30¹⁻⁴.
- To determine and compare patterns of disease recurrence between the two therapeutic approaches and their clinical implications.

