3.10. Off Study Criteria

- Death

- Unwillingness to participate in study specified follow up (including phone contact)
- If the physician deems it is no longer in the best interest of the patient to remain on study

Note: As the objective of this study is overall survival, every attempt will be made to follow patients for life.

Patients will be officially taken off study by contacting the CRO.

3.11.Measurement of Health Related Quality of Life

Baseline Quality of Life Questionnaires (QOL) will be completed prior to randomization, prior to cycle 9 of chemotherapy and then every 12 weeks (+/- 2 weeks) for the first 2 years, every 6 months for the next 3 years, and yearly thereafter. (Note: patients who begin chemotherapy >5 weeks following randomization will be asked to complete the QOL prior to the first cycle of chemotherapy.

Patients will be informed of the details of the QOL part of this study and reassured that their decision to participate will not affect their participation in the either of the treatment arms of this protocol. Once enrolled, the patient has the right at any time to elect not to continue completing the questionnaires. In the event a patient goes off study prior to completion of the follow up time points, the data gathered from their completed QOL questionnaires will be included in the final analysis.

To QOL parameters and quality of life adjusted survival between the two study groups, we will use tools specifically developed for assessment of QOL in gastric cancer patients: FACT-Ga, ; Blazeby JM, Eur J cancer 2004 (Appendix 6). Measures will be initially administered by the Associate Investigator Research Nurse or designee prior to randomization. The Research Nurse will assess the patient's ability to read, and if the patient is unable to read, it will not be administered. The Research Nurse or designee will administer the questionnaires providing a firm surface at a table or a clipboard and a pencil. The patients will be directed to complete the questionnaires using the following instructions:

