The evaluation for better than expected efficacy will be performed as follows. Beginning at the first annual DSMB meeting after 68 patients have been randomized, annual interim evaluations will be performed to determine if there is sufficient evidence to terminate accrual because of a better than expected improvement in overall survival. An alpha spending function approach to monitoring will take place using an O'Brien-Fleming interim evaluation boundary ⁷⁹. It will be assumed that a total of 121 deaths would take place over a total of 8 years of accrual plus monitoring, and that monitoring would begin after approximately 40-45 deaths have been noted. The information fraction used to compute the interim boundary at each annual evaluation will be calculated as the number of patients who died /121.

Quality of life evaluations will be compared between the two study arms, with comparisons at multiple individual time points, as well as with respect to changes from baseline. Wilcoxon rank sum tests will likely be used. The evaluation will be considered secondary, and p-values resulting from the analysis will be presented without adjustment for multiple comparisons, but in the context of the number of tests evaluated.

It is expected that 24 patients per year can be accrued onto this trial, and thus accrual will be completed in approximately 6 years. Allowing for a very small number of inevaluable patients, the accrual ceiling will be set at 140 patients.

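### Section 5.4 compares quality of life visit by visit with no rule for death, so in practice among surviving form-completers, and contains no analysis of the quality-adjusted survival named in 3.11

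*Combined protocol and SAP*

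**What the plan says.** The secondary objective in section 1.1.2 is "To compare quality of life (QOL) parameters between the two study groups". Quality-adjusted survival is not mentioned there.

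Section 3.11 names a second outcome, in a sentence that has lost its verb: "To QOL parameters and quality of life adjusted survival between the two study groups". No weights, time horizon or method for it appear anywhere.

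Forms are due before randomization, then "prior to cycle 9 of chemotherapy and then every 12 weeks (+/- 2 weeks) for the first 2 years", and less often after that. For a patient who goes off study, "the data gathered from their completed QOL questionnaires will be included in the final analysis". Section 3.10 lists death as an off-study criterion.

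Section 5.4 plans between-arm QOL comparisons "with comparisons at multiple individual time points, as well as with respect to changes from baseline". On method it says "Wilcoxon rank sum tests will likely be used". The analysis is secondary, and "p-values resulting from the analysis will be presented without adjustment for multiple comparisons, but in the context of the number of tests evaluated". Section 5.4 has no rule for deaths or for missing forms, and no quality-adjusted survival analysis.

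**The concern.** A patient who has died has no form at later visits. With nothing said about death, the natural reading is that each visit's test uses whoever is alive and responds. If the arms differ in survival, as the design assumes, the two groups tested at a visit have been selected to different degrees. A difference in scores, or the lack of one, then mixes the effect on QOL with the effect on who is still there to report it. The selection grows with time and recurs at every visit.

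What is at stake is the answer to the QOL objective. Whether major surgery costs patients quality of life is central to interpreting this trial. The one outcome in the protocol that would keep every randomized patient in the comparison, quality-adjusted survival, has no analysis.

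**Working it through.** **1. The plan's own figures.** Section 5.4 gives medians of 12 months (SA) and 20 months (GYMS), exponential survival, 68 per arm, and 12-month survival of 50% and 66%. With hazards ln2/12 = 0.0578 and ln2/20 = 0.0347, 12-month survival is exp(-0.0578 x 12) = 0.500 and exp(-0.0347 x 12) = 0.660, as stated. The stated 121 deaths also reproduce: the Schoenfeld formula for a hazard ratio of 20/12 gives 121 events, with power 0.802. Uniform accrual over 72 months plus 24 months of follow-up gives 121.1 expected deaths among 136 patients.

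**2. Who is left to compare.** Survival at t months is 2^(-t/12) in SA and 2^(-t/20) in GYMS, multiplied by 68:

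| Months | SA alive | GYMS alive |
|---|---|---|
| 6 | 0.707, 48 | 0.812, 55 |
| 12 | 0.500, 34 | 0.660, 45 |
| 24 | 0.250, 17 | 0.435, 30 |
| 36 | 0.125, 8.5 | 0.287, 19.5 |

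These are upper limits on the numbers analysed, because some living patients will not return forms.

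**3. Size of the bias if the survival benefit is common to all.** The documents give no correlation between QOL and survival, so every value here is an assumption. In all cases QOL has the same distribution in both arms at randomization, so any difference among survivors is bias. Differences are GYMS minus SA in SD units.

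- *Frailty model.* Log-normal frailty with a log-hazard slope of 0.5-1.0 per SD, QOL correlated 0.5-0.7 with frailty, marginal medians 12 and 20 months, 3,000 simulated trials per scenario. Across 12 and 24 months the difference is about -0.05 to -0.14 SD. A significant result for SA arises in about 4-8% of trials, against a nominal 2.5%.
- *Copula model.* Exponential death times joined to QOL by a Gaussian copula, 2,000 simulated trials:

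| Correlation | 12 months: difference, two-sided rejection | 24 months: difference, two-sided rejection |
|---|---|---|
| 0 | 0.00, 4% | 0.01, 5% |
| 0.3 | -0.08, 7% | -0.12, 5% |
| 0.5 | -0.11, 8% | -0.18, 9% |
| 0.7 | -0.17, 13% | -0.26, 16% |

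Once the correlation exceeds zero, most rejections are against GYMS. Simulation error is about 1 percentage point.

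**4. If the benefit is not common.** These are large-sample runs of the copula model with correlation 0.3-0.5 and the GYMS median held at 20 months. If only patients with poorer QOL gain survival, the difference is -0.26 to -0.30 SD at 12 months and -0.48 to -0.55 SD at 24 months. If only patients with better QOL gain survival, the sign reverses: +0.05 to +0.10 SD at 12 months and +0.04 to +0.18 SD at 24 months.

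**5. Change from baseline.** In the frailty model, treat QOL as a stable trait with an assumed baseline-to-follow-up correlation of 0.7. The change-score difference is then within 0.01 SD of zero, and results for SA stay near the nominal 2.5%. If instead it is the decline in QOL that tracks death, change scores carry much the same bias as raw scores, -0.05 to -0.11 SD.

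**6. Two ways to keep all randomized patients.**

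- *Death ranked worst in the Wilcoxon test.* With no QOL difference, the copula model rejects (two-sided) in about 24-39% of trials at 12 months and 50-61% at 24 months. The frailty model finds for GYMS in about 20-48%. The test is largely detecting survival.
- *Quality-adjusted survival to 24 months.* Mean survival restricted to 24 months is (1 - 0.250)/0.0578 = 12.98 months in SA and (1 - 0.435)/0.0347 = 16.29 months in GYMS, a difference of 3.31 months. With an assumed common weight of 0.5 to 0.9, that is 3.31 x 0.5 = 1.7 to 3.31 x 0.9 = 3.0 quality-adjusted months. This measure also contains survival, but openly and in interpretable units.

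**The case against.** The strongest reply is that the direction cannot be known. A reader might infer that if surgery prolongs life, the planned tests must be biased against it. The documents do not support that. It needs poor QOL to predict death, and a benefit that is common or reaches the frail. Section 1.1.2 sets out to find both patients who may benefit from surgery and patients who will not, so the protocol itself expects unequal benefit. Step 4 shows that the sign can reverse. This objection stands in full. It does not rescue the comparison, because a bias of unknown sign still leaves the QOL objective unanswered.

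Second, changes from baseline are also planned, and they remove the bias if QOL is a stable trait. That is correct under that assumption, but the protection fails if decline precedes death, and the plan does not argue for either case.

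Third, the text should not be over-read. Section 5.4 is silent on deaths and does not say that they are dropped, and the Wilcoxon test is only likely. One incomplete sentence in 3.11 names quality-adjusted survival but hardly promises it. All of this stands. What remains is an unspecified handling of death and two sections that do not match.

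Fourth, the endpoint is secondary, p-values are to be read against the number of tests, and a shift of about a tenth of an SD is small. That limits the severity. It also means that a claim that the QOL conclusion would run opposite to patients' experience is not supported.

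**Conclusion.** The point holds in a limited form. Section 5.4 has no rule for death, so in practice its time-point and change-score comparisons are made among surviving form-completers: at most about 34 v 45 patients at 12 months and 17 v 30 at 24 months if the design assumptions hold. They do not compare the randomized arms and can be biased.

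Against GYMS, the bias is about 0.05-0.15 SD if poorer or declining QOL predicts death and the benefit is common. A stronger assumed dependence in the copula model takes it to 0.26 SD at 24 months. It is zero if QOL and survival are unrelated, and it favours GYMS if only fitter patients gain. Which case applies cannot be settled from the documents, since the link between QOL and survival is assumed throughout.

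Separately, the quality-adjusted survival named in 3.11 has no counterpart in 5.4. The primary survival analysis, sample size and monitoring rules are untouched. This is a worthwhile, inexpensive improvement to a secondary analysis.

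**What to change.** - **Add to 5.4** a between-arm comparison of quality-adjusted survival in all randomized patients: survival weighted by a prespecified 0-1 scaling of the QOL score, to a fixed horizon such as 24 months, with a bootstrap interval. Follow-up of 2 years after the last entry covers that horizon. State which instrument supplies the weight, and how scores are carried between forms and handled when a living patient's form is missing. The early forms are tied to chemotherapy cycles, so they fall at different times since randomization in the two arms.
- **Complete the sentence in 3.11** so that it matches this analysis.
- **Label the time-point and change-score Wilcoxon tests** as descriptive among survivors, and report for each visit and arm the number alive and the number completing forms.
- **Use a death-ranked-worst Wilcoxon test only as a sensitivity analysis**, labelled as a composite of survival and QOL. As the main QOL comparison it would largely retest the primary endpoint.

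The cost is a little more analysis on data already to be collected. The drawback is that the result depends on the chosen weights, which can be varied in a sensitivity analysis.

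### Quality of life is to be tested on raw scores and on change scores; making a rank-based analysis adjusted for the pre-randomisation score the primary comparison would be a cheap gain in precision

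*Combined protocol and SAP*

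**What the plan says.** Section 1.1.2 lists among the secondary objectives: "To compare quality of life (QOL) parameters between the two study groups". Section 5.4 describes the analysis in a few lines. The arms are compared "with comparisons at multiple individual time points, as well as with respect to changes from baseline. Wilcoxon rank sum tests will likely be used". No covariate and no longitudinal model is named. On status and multiplicity it states: "The evaluation will be considered secondary, and p-values resulting from the analysis will be presented without adjustment for multiple comparisons", and it adds that the p-values will be read against the number of tests made.

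Section 3.11 fixes the timing: "Baseline Quality of Life Questionnaires (QOL) will be completed prior to randomization, prior to cycle 9 of chemotherapy", with a 12-weekly schedule for two years and longer intervals after that. One further questionnaire is conditional: "patients who begin chemotherapy >5 weeks following randomization will be asked to complete the QOL prior to the first cycle of chemotherapy". Completing the questionnaires is optional, and they are not given to patients who cannot read.

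The documents state no standard deviation, target difference, correlation or power for QOL.

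**The concern.** Write r for the correlation between a patient's baseline and follow-up scores. A raw-score comparison subtracts none of the baseline. A change-score comparison subtracts all of it. The efficient amount is the fraction r, so for any r strictly between 0 and 1 both planned analyses are less precise than one that adjusts for the baseline. Change scores also carry chance baseline imbalance into the result, because with equal SDs the covariance of the change with the baseline is r − 1, which is negative.

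The valid covariate is already being collected, before randomisation, in every patient who takes part in the QOL component. The sample available for QOL shrinks quickly as patients die, so there is little precision to spare on a listed objective. Running both analyses, with the test described only as likely, also leaves open which result will be emphasised.

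**Working it through.** **The plan's own figures.** There is no QOL calculation to reproduce, so I checked the survival assumptions that determine how many patients remain. With medians of 12 and 20 months the hazard ratio is 20/12 = 1.667. Schoenfeld's formula gives 4 × (1.960 + 0.842)² / (ln 1.667)² = 120.3, so 121 deaths, as Section 5.4 states. With exponential survival, 72 months of uniform accrual and 24 further months, the probabilities of death are 0.941 (SA) and 0.840 (GYMS). Then 68 × (0.941 + 0.840) ≈ 121 deaths. The stated design reproduces.

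**Patients available for QOL.** These counts assume that every survivor responds, so they are upper bounds.
- 12 months: SA 68 × 2^(−12/12) = 34; GYMS 68 × 2^(−12/20) = 44.9, about 45.
- 24 months: SA 68 × 2^(−24/12) = 17; GYMS 68 × 2^(−24/20) = 29.6, about 30.

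**Variance.** Take equal SDs at baseline and follow-up, and set the raw-score variance to 1. The change score has variance 1 + 1 − 2r = 2(1 − r). The baseline-adjusted score has 1 − r². The reduction from adjustment is therefore r² against raw scores and 1 − (1 − r²)/[2(1 − r)] = (1 − r)/2 against change scores.

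| r (assumed) | raw | change | adjusted | cut v raw | cut v change | cut v better planned |
|---|---|---|---|---|---|---|
| 0.3 | 1 | 1.40 | 0.91 | 9% | 35% | 9% |
| 0.5 | 1 | 1.00 | 0.75 | 25% | 25% | 25% |
| 0.7 | 1 | 0.60 | 0.51 | 49% | 15% | 15% |

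Against the better planned analysis the gain is r² up to r = 0.5 and (1 − r)/2 beyond it, so 25% is the maximum.

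**Power, normal scores.** Simulation with 34 v 45 patients, an assumed 0.5 SD difference and a two-sided 0.05 test:

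| r | Wilcoxon raw | Wilcoxon change | linear ANCOVA | rank ANCOVA | rank ANCOVA minus better planned |
|---|---|---|---|---|---|
| 0.3 | 57% | 42% | 62% | 60% | 3 |
| 0.5 | 57% | 55% | 71% | 67% | 10 |
| 0.7 | 56% | 77% | 86% | 82% | 5 |

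A repeat with other random numbers gave rank-ANCOVA gains of 4, 11 and 4 points, and another gave about 2, 11 and 3. Each used 3,000 or 4,000 runs. The simulation standard error of one power figure is at most √(0.25/3000) = 0.9 points. Type I error was close to 5% for all four methods.

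**Power, skewed scores.** Same setting, with an assumed lognormal shape (sigma 0.8). At r = 0.3, 0.5 and 0.7, raw Wilcoxon has about 94%, 93% and 93%, and linear ANCOVA only 66%, 71% and 82%. Rank ANCOVA has 96% to 99%. At r = 0.7 the change-score Wilcoxon, at about 96% in a check run, is the better planned test, so the margin there is about 3 points. Overall the gain is about 2 to 4 points; at r = 0.3 some runs gave only about 1 (95% v 94%).

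**Which score is the baseline.** Section 3.5.1 starts SA chemotherapy within 14 days of randomisation (6 to 8 weeks after palliative gastrectomy) and GYMS chemotherapy about 6 to 8 weeks after surgery. The conditional pre-cycle-1 questionnaire therefore falls mostly on GYMS patients, after randomisation and after surgery. Using it as baseline would remove part of the treatment effect in one arm only.

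**The case against.** The strongest reply is that nothing here is wrong. QOL is secondary and unpowered, the plan says so, and distribution-free tests are a legitimate choice for such scores. The wording is provisional: "Wilcoxon rank sum tests will likely be used". The primary analysis is untouched. All of that stands, and it limits this point to an improvement. The provisional wording is also a reason to name one primary comparison before the data are seen.

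A second reply is that comparing Wilcoxon with linear ANCOVA on normal data credits baseline adjustment with a gain that comes partly from dropping ranks. This also stands. Like for like, rank against rank, the gain is smaller, and on skewed scores linear ANCOVA does worse than the planned raw-score test. The recommendation is therefore the rank-based version.

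A third reply is that multiplicity is already disclosed. That is correct: the plan undertakes to present p-values in the context of the number of tests, so the double testing is not hidden.

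A reader might infer that adjustment recovers a quarter of the variance at no cost. The documents do not support that. The quarter needs r = 0.5, which they do not give and which is the most favourable value against the better planned test. There is also a cost, since some patients may have no baseline score. Nor are both planned analyses unadjusted in the same sense: the change score does use the baseline, and at r = 0.7 it is far more powerful than the raw score (77% v 56%).

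**Conclusion.** The point holds as a cheap gain in precision on a secondary objective. Across assumed correlations of 0.3 to 0.7, the variance reduction is 9% to 25% against the better of the two planned analyses. In power, rank-based ANCOVA adds about 3 to 11 points on normal scores and about 2 to 4 on skewed ones. These figures rest on an assumed correlation, an assumed 0.5 SD difference, the assumed score shapes, and 34 and 45 respondents at 12 months, which is an upper bound.

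Two stronger conclusions are tempting and should not be drawn. The planned tests are not invalid; they held their type I error in simulation. And baseline adjustment does not deal with the dominant difficulty in this endpoint, which is that survivors differ in number between arms (34 v 45 at 12 months, 17 v 30 at 24) and may differ in kind. Any comparison at a time point describes patients alive and responding then. The log-rank design is unaffected.

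**What to change.** In Section 5.4, replace the sentences on the QOL comparison and test with wording such as:

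> At each time point QOL scores will be compared between arms by rank-based ANCOVA with the pre-randomisation score as covariate, among patients alive and responding at that time, with one primary comparison per scale and time point. The questionnaire taken after randomisation and before cycle 1 will not be used as the baseline. Wilcoxon tests on raw scores and on changes are sensitivity analyses, and include patients without a baseline where possible.

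The existing statement on secondary status and unadjusted p-values can stay.

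The cost is a change of text and slightly more programming, with no new data. Patients with no baseline score, because they could not read the form or declined it, drop out of the adjusted analysis. The raw-score sensitivity analysis keeps those with a follow-up score, and their number should be reported by arm.
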